5. STUDY DESIGN

5.1. Overall Design

This study is a randomized, placebo-controlled, double-blind (sponsor unblind), parallel group, multi-center phase IIa trial in two equal sized cohorts (male or female). Following completion of screen assessments, baseline assessments will be conducted in eligible participants and, in each cohort, the participants will be randomized 1:1 to GSK2881078 or matching placebo.

Figure 1 Study Schematic

This study will assess the effect of GSK2881078 on physical strength and function after 13 weeks of treatment. The placebo group will serve as an appropriate control group in order to limit evaluation bias in the study endpoints. No suitable active comparator is currently available. Both treatment and control groups will be asked to participate in a standardized home exercise program. Study treatment will consist of two dosing cohorts (Male: placebo or 2.0 mg of GSK2881078; Postmenopausal female: placebo or 1.0 mg of GSK2881078). All participants will take their first dose of study treatment in the clinic following randomization, and will continue on a once daily dose for the duration of the treatment period. Participants will be dosed without regards to food intake. All doses should be administered in the clinic on study visit days during the treatment period. Time of dosing for the 2 doses prior to sample collection should be recorded and PK samples should be collected as specified in the SoA (Section 2).

The study will consist of a screening/baseline period of up to 30 days, a 13-week treatment period, and a 6-weeks post-treatment follow-up visit as described in the Time and Events table (Section 2). Unscheduled visits may be performed as needed to conduct optional assessments required to follow unresolved findings of clinical concern.

Participants will participate in a screening visit within 30 days prior to randomization and baseline assessments. Prior to randomization, eligible participants will need to have a functional muscle deficit as defined by the Short Physical Performance Battery (SPPB) inclusion criterion (Section 6.1). Eligible participants will also have physical activity and patient reported outcomes (PROs) recorded prior to baseline, and will need to

demonstrate compliance with completion of the electronic diaries and wearing the activity monitor prior to randomization.

The selection of individual medications and dosages for the treatment of COPD is left to the discretion of the investigator, although it is recommended that treatment regimens conform to current, local, national standard of care, and that treatment is optimized prior to screening with no further changes to treatment anticipated between the randomization visit and the end of the study.

Eligible participants will be randomized as described above following completion of the Baseline assessments. Participants will be sent home with a 42-day supply of study medication. Participants will be asked to return to the clinical unit on approximately days 14, 28, 56, 80 and 90 as specified in the SoA (Section 2) Participants will be resupplied with study treatment at the Day 28 and 56 visits.

All visits should be conducted in a single day within the study visit window (Section 2). Participants will be provided a meal between completion of fasting labs and start of other study assessments.

All participants will be asked to participate in a home exercise program reflecting usual care (e.g. a pulmonary rehabilitation program). The home exercise program will consist of daily walking, along with several resistance or weight-bearing exercises, such as bicep curls, upright rows, step ups, and a sit-to-stand manoeuvre, as allowed by site staff at screening. Site staff will supervise performance of the initial exercises to assess which of the four exercises can be prescribed to participants, as well as setting the baseline intensity for the exercises and clarifying instructions from the home exercise Application. Home exercises will be monitored with the use of a consumer-based activity monitor during the activities outside the clinic [Mitchell, 2014]. Guidance for performing exercises and setting goals will be given by the home exercise Application from the baseline visit onwards, however participants will have the opportunity to raise any concerns they have with site staff. See Study Reference Manual (SRM) for additional detail.

A physical activity monitor will be worn for 7 days at screening for eligible participants, 7 days after the Day -9 visit, for 7 days after the Day 56 visit, and for 7 days following the day 80 visit. During those periods, participants will rate their physical activity on a daily basis by completing the PROactive eDiary. In addition, participants will be asked to complete additional questionnaires CAT which assesses the impact of COPD on a patient's life, Patient Global Rating of Severity (PGRS), Patient Global Impression of Change (PGIC) during scheduled clinic visits as specified in the SoA Time and Events table (Section 2).

Participants will return to the clinic for a follow-up visit 42 days (± 7 days) after the final dose of study treatment to undergo safety evaluations and final functional assessments. In addition, all remaining study medication that was not returned at the last treatment visit (i.e., Day 90) will be returned to the clinical unit for final drug accountability.

The study duration, including screening and follow-up, is not expected to exceed 6 months for participants in the study.

Unblinded data will be reviewed in-stream by the GSK clinical study team and the safety review team (SRT). If, at any time, the 2.0 mg dose in men or the 1.0 mg dose in women, has a safety signal of clinical concern, treatment will be stopped.

An interim analysis for the assessment of futility is planned. It is anticipated that a formal declaration of futility would not be made before at least 10 participants per group have completed dosing and all key study assessments. However, if at any time it is determined that the probability of a successful outcome is sufficiently low, recruitment could be stopped. The primary endpoint for assessment of futility is strength. However, the decision to continue or stop recruitment will be made by the unblinded GSK clinical study team and Safety Review Team (SRT) based on the evaluation of all available safety, efficacy, and tolerability data. Such decisions will be based on the totality of the data (including strength, lean mass, function, safety, and tolerability). See Section 10 for more detail. The feasibility of making a decision to stop recruitment based on a futility analysis will be dependent on the recruitment rate. Futility will be evaluated separately for female and male participants.

Based on the observed variability and treatment effects at an interim analysis, the sample size may be increased to improve the precision of the estimates of treatment effects. This will be evaluated separately for males and females. The sample size may be increased by up to 15 subjects/arm.

5.2. Number of Participants

At least 100 participants with COPD and muscle weakness will be randomized (25/arm) to target approximately 80 evaluable participants (20/arm). Men and women will be recruited into separate cohorts of at least 50 participants each, with each cohort containing a placebo and GSK2881078 arm. Sample size consideration and assumptions are discussed in more detail in Section 10.1.1 .

Within each cohort, equal numbers of male and female participants will be randomized in a 1:1 allocation using a central randomization system to receive one of the planned treatment regimens listed below:

Male participants: Placebo or 2.0 mg GSK2881078

Female participants: Placebo or 1.0 mg GSK2881078

Additional participants may be enrolled if the number of participants with exacerbations plus the number of participants withdrawn prematurely for other reasons is higher than anticipated (approximately 20%), or the precision of the estimates of the treatment effects based on the observed variability and treatment effect at an interim analysis. The total sample size may be increased by up to 60 participants (approximately 15/arm). Enrolment is not expected to exceed approximately 160 total participants.

5.3. Participant and Study Completion

A participant is considered to have completed the study if they have completed all phases of the study including the follow-up visit.

The end of the study is defined as the last participant's last visit.

5.4. Scientific Rationale for Study Design

This study is designed as a proof of concept study to evaluate the anabolic potency of GSK2881078 using leg strength as the primary endpoint. This endpoint has been used in several studies with testosterone, including dose response studies in men, with a good correlation between anabolic potency and change from baseline in leg strength [Bhasin, 2005]. In addition, functional endpoints, defined as short physical performance battery, incremental and endurance shuttle walk, and PRO, are included. The duration of the study, 13 weeks, is adequate to reach a near plateau effect in leg strength [Sheffield-Moore, 2011].

Based on studies with testosterone [Casaburi, 2004 ; Sheffield-Moore, 2011] it is estimated that a minimum of 2kg increase in total LBM would be needed to achieve a meaningful improvement in leg strength. The amount of muscle mass change required to elicit meaningful functional change in humans is unknown.

5.5. Dose Justification

GSK2881078 has been administered to 154 subjects across two clinical pharmacology studies in healthy human volunteers (study 200181 in healthy young men and post-menopausal women and study 204699 in healthy elderly men and post-menopausal women). PK and pharmacodynamic (PD) of GSK2881078 have been evaluated over the range of 0.05 mg to 4.0 mg in men and 0.24 mg to 1.5 mg in women for up to 56 days duration. PK data suggests that GSK2881078 has a long half-life in the range of 5-8 days.

From an efficacy and safety standpoint, significant gains in lean mass from baseline have been observed across the dose levels evaluated to date with women showing greater sensitivity to the anabolic stimulus than men. Total mean body lean mass accrual in phase I studies ranged between 0.43kg and 3.39kg for women and 0.87kg and 1.72kg for men across different doses. PD analysis from phase I suggests that a 1.0mg dose in women would achieve a total lean mass accrual of approximately 2kg. In males, a plateau appeared to have been reached between the 1.5mg and 4mg doses, therefore a dose of 2.0mg was chosen.

From a safety coverage standpoint, the exposures as measured by area under the concentration-time curve over the dosing interval (AUC[0- τ]) at the 2.0 mg dose in men and 1.0 mg dose in postmenopausal women represent <50% of NOAEL established in the 13-week dog study in both genders, respectively. The dose limiting toxicity observed in the 13-week dog study was at 2 mg/kg/day, the highest dose given. At 2 mg/kg/day on Day 91, mean systemic exposure values were area under the concentration-time curve from time zero (pre-dose) to last time of quantifiable concentration within a participant across all treatments (AUC_{0-t}) 10.8 μ g.h/mL for male dogs and 6.46 μ g.h/mL for female dogs, and maximum observed concentration (C_{max}) 0.778 μ g/mL for male dogs and 0.536 μ g/mL for female dogs).

GSK2881078 has been generally well tolerated with no SAEs noted. Adverse events of potential clinical significance primarily related to clinical chemistry including elevations of liver function tests, HDL cholesterol lowering, and suppression of testosterone and sex hormone binding globulin (SHBG). Elevations of liver function tests appeared transient, and changes in HDL, testosterone and SHBG were reversible on treatment discontinuation. Results of drug interaction study in healthy volunteers conducted with a prototype strong CYP3A4 inhibitor (itraconazole) showed that exposure to GSK2881078 was only modestly elevated when co-administered with a strong CYP3A4 inhibitor (AUC(0-∞) increased by 60% while Cmax decreased by 21%) compared to given alone. Therefore, exposure to GSK2881078 is expected to be within the safety margin at the proposed dose of 1 mg in women and 2 mg in men if a CYP3A4 inhibitor is co-administered with GSK2881078.

6. STUDY POPULATION

Prospective approval of protocol deviations to recruitment and enrolment criteria, also known as protocol waivers or exemptions, is not permitted.

Deviations from inclusion and exclusion criteria are not allowed because they can potentially jeopardize the scientific integrity of the study, regulatory acceptability, or participant safety. Therefore, adherence to the criteria as specified in the protocol is essential. Specific information regarding warnings, precautions, contraindications, AEs, and other pertinent information on the GSK investigational product or other study treatment that may impact participant eligibility is provided in the IB/IB supplement(s).

6.1. Inclusion Criteria

Participants are eligible to be included in the study only if all of the following criteria apply:

1. Participant must be 50 to 75 years of age inclusive, at the time of signing the informed consent.
2. Male and/or female:

a. Male participants:

A male participant with a partner who is a woman of child bearing potential (WOCPB) must agree to use contraception as detailed in [Appendix 2](#) of this protocol during the treatment period and for at least 5 half-lives of study medication have passed after the last ingested dose [125 days, corresponding to time needed to eliminate study treatment for both genotoxic and teratogenic study treatments *plus* an additional 90 days (a spermatogenesis cycle) for study treatments with genotoxic potential] after the last dose of study treatment and refrain from donating sperm during this period.

b. Female participants:

A female participant is eligible to participate if she is post-menopausal and not a woman of childbearing potential (WOCBP) as defined in [Appendix 2](#). Note: Postmenopausal is defined as 12 months of spontaneous amenorrhea [in questionable

cases a blood sample with simultaneous follicle stimulating hormone (FSH) levels consistent with menopause (refer to laboratory reference ranges for confirmatory levels), or be >60 years of age].

3. Confirmed diagnosis of COPD in accordance with the ATS/ERS criteria [Celli, 2004] with a post-bronchodilator FEV₁/ forced vital capacity (FVC) < 0.70 AND 30% ≤ FEV₁%predicted ≤65% of predicted normal value calculated at Screen using the Quanjer reference equation [Quanjer, 2012].
4. Short Physical Performance Battery (SPPB) with ALL of the following:
 - Timed chair stand score ≥1 AND ≤3
 - No score of “0” on any component of the SPPB (i.e., gait speed, balance, or timed chair stand)
5. Body Mass Index (BMI) within the range 18 - 32kg/ m² (inclusive), where BMI = (weight in kg) / (height in meters)²
6. Current smokers OR former smokers with a cigarette smoking history of ≥10 pack years (1 pack year =20 cigarettes smoked per day for 1 year or equivalent). Former smokers are defined as those who have stopped smoking for at least 6 months prior to Baseline.
7. Participants must be able to read and write in the language used for the provided electronic diary and be able to operate an electronic device to a level that allows them to complete an electronic diary on a daily basis.
8. Participants participating in a structured exercise program must be willing to convert their current exercise program to the home exercise program used in this study.
9. Capable of giving signed informed consent as described in [Appendix 3](#) which includes compliance with the requirements and restrictions listed in the informed consent form (ICF) and in this protocol.

6.2. Exclusion Criteria

Participants are excluded from the study if any of the following criteria apply:

Medical Conditions

1. Participants with a history of myocardial infarction, angina, congestive heart failure exacerbation, hospitalization for cardiac aetiology, stroke or transient ischemic attack in the past 12 months.
2. Neurologic, musculoskeletal, osteoarthritis, or any other condition that in the opinion of the investigator limits participant's ability to complete study physical assessments.
3. Current or chronic history of liver disease, or known hepatic or biliary abnormalities (with the exception of Gilbert's syndrome or asymptomatic gallstones).
4. Participants with a history of cholecystectomy.
5. Participants with a history of malignancy that is not in complete remission for at least 2 years or 1 year for non-melanoma skin carcinoma.
6. Participants with a family history of early onset prostate cancer or familial prostate cancer (multiple family members).

7. Diseases known to cause malabsorption of protein or energy, such as inflammatory bowel disease, celiac disease, pancreatic insufficiency, etc.

Prior/Concomitant Therapy

8. Current or planned administration of cholestyramine or strong oral or injectable cytochrome P-450 isoenzyme 3A4 (CYP3A4) inducers (refer to Section 7.7 for a list of prohibited medications).
9. Current or planned use of any prescription drugs known to affect muscle mass, including androgen supplements, anti-androgens (such as LHRH agonists), anti-estrogens (tamoxifen, etc.), recombinant growth hormone, megestrol, etc.
10. Use of oral steroids concurrently or within 4 weeks preceding the screening visit.

Prior/Concurrent Clinical Study Experience

11. The participant has participated in a clinical trial and has received an investigational product within the following time period prior to randomization in the current study: 30 days, 5 half-lives or twice the duration of the biological effect of the investigational product (whichever is longer).

Diagnostic assessments

12. Participants with values outside the specified ranges for the following Key Clinical Laboratory Tests must be excluded from the study:
 - Renal function: Glomerular Filtration Rate (GFR) <30 (mL/min/1.73 m²) using formulae provided in the Study Reference Manual (SRM). Note: Participants receiving dialysis are excluded from this study.
 - Metabolic – HbA1c $>7.5\%$.
 - ALT $>2\times$ ULN and bilirubin $>1.5\times$ ULN (isolated bilirubin $>1.5\times$ ULN is acceptable if bilirubin is fractionated and direct bilirubin $<35\%$).
 - Haematology – Haemoglobin <10.0 g/dL at screening
 - Prostate Specific Antigen (PSA) >4.0 ng/mL
13. Presence of hepatitis B surface antigen (HBsAg), positive hepatitis C antibody test result at screening or within 3 months prior to first dose of study treatment. NOTE: Participants with positive Hepatitis C antibody due to prior resolved disease can be enrolled, only if a confirmatory negative Hepatitis C RNA PCR test is obtained.
14. QT interval corrected for heart rate by Bazett's formula (QTcB) or QT interval corrected for heart rate by Fridericia's formula (QTcF) >450 msec or QT interval corrected for heart rate (QTc) >480 msec in participants with Bundle Branch Block based on a single ECG.
15. A positive test for HIV antibody.

Other Exclusions

16. More than two moderate/severe COPD exacerbations within the past year
 - Exacerbation is defined as worsening of two or more of the following major symptoms: dyspnoea, sputum volume, sputum purulence OR worsening of any one major symptom together with at least one of the following additional symptoms: sore throat, colds (nasal discharge and/or nasal congestion), fever $> 37.5^{\circ}\text{C}$ without any explained cause, increased cough, increased wheeze.
 - A moderate exacerbation is defined as an exacerbation that requires treatment with antibiotics and/or oral steroids. A severe exacerbation is defined as an event that is additionally associated with hospitalization or emergency room visit.
17. Any moderate/severe COPD exacerbation in the 4 weeks preceding the screening visit.
18. Participants on long term oxygen therapy (LTOT), defined as prescribed continuous oxygen use for >14 hours/day.
19. Clinically diagnosed history of drug or alcohol abuse within 5 years prior to randomization.
20. History of sensitivity to any of the study medications, or components thereof or a history of drug or other allergy that, in the opinion of the investigator or GSK Medical Monitor, contraindicates their participation.
21. Participation in a formal pulmonary rehabilitation exercise program outside or inside the home, either currently or completed within the previous 6 months.
22. For participants who opt to have MRI at participating study sites, there must be no contraindications to MRI, for example known claustrophobia or a pacemaker. Specific MRI contraindications will be determined by the type of MRI scanner available at each site and study personnel should confirm local eligibility requirements.

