3.3.1. Risk Assessment

Potential Risk of Clinical Significance	Summary of Data/Rationale for Risk	Mitigation Strategy
Investigational Product (IP) GSK2881078		

Elevation of Alanine Aminotransferase (ALT) and other liver function tests (AST, bilirubin, total and direct).
	
This has been observed in a variety of SARMs and was observed (minimal) in the 14-day and 13-week rat toxicity studies with administered GSK2881078.
 
One subject had elevations of Liver Function Tests (LFTs) in Phase 1a, but it was unclear if this was related to drug. Transient elevations in ALT without concomitant changes in bilirubin were observed in Phase 1b.
	
Monitoring of liver function tests will be in place at all clinic visits. This study will use follow up procedure that were used in Phase I of development of GSK2881078 for participants who have met liver stopping criteria, as detailed in Section 8.1.1 of this protocol.

Effects on reproductive organs/tissues:
 
Men – testes, epididymis, and prostate gland
 
Women – ovaries and uterus
	
These are recognized effects of SARM pharmacology and show recovery on discontinuation of dosing.
 
Test article-related organ weight and/or microscopic changes were observed in the gonads and other associated reproductive tissues in rat 14-day and 13-week toxicity studies administered GSK2881078. All test article-related microscopic findings were reversible after a 4- or 8- week off dose period. Test article-related effects were observed in male mating, fertility, gonadal function, and male-mediated development in a male rat fertility study.
 
In phase I studies, all male subjects dosed with
	
Males with PSA levels >4.0 ng/mL will be excluded.
 
Females will be post-menopausal.
 
Participants will be monitored at baseline, Day 28, Day 56, Day 89 and follow-up for changes in the following levels:
 
 • luteinizing hormone • follicle stimulating hormone • testosterone • free testosterone (calculated) • estradiol

Potential Risk of Clinical Significance	Summary of Data/Rationale for Risk	Mitigation Strategy

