9. STUDY ASSESSMENTS AND PROCEDURES

- Study procedures and their timing are summarized in the SoA.
- Protocol waivers or exemptions are not allowed
- Immediate safety concerns should be discussed with the sponsor immediately upon occurrence or awareness to determine if the participant should continue or discontinue study treatment.
- Adherence to the study design requirements, including those specified in the SoA, is essential and required for study conduct.
- All screening evaluations must be completed and reviewed to confirm that potential participants meet all eligibility criteria. The investigator will maintain a screening log to record details of all participants screened and to confirm eligibility or record reasons for screening failure, as applicable.
- Except for the SPPB, procedures conducted as part of the participant's routine clinical management (e.g., blood count) and obtained before signing of ICF may be utilized for screening or baseline purposes provided the procedure met the protocol-specified criteria and was performed within the time frame defined in the SoA. All protocol-specified lab samples obtained from Baseline through the end of the study must be submitted to the central lab.
- The maximum amount of blood collected from each participant over the duration of the study, including any extra assessments that may be required, will not exceed 500 mL. Individual visit blood draws should not exceed 50mls. Repeat or unscheduled samples may be taken for safety reasons or for technical issues with the samples.

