12.4. Appendix 4: Liver Safety: Required Actions and Follow-up Assessments

Liver chemistry stopping and increased monitoring criteria have been designed to assure subject safety and evaluate liver event aetiology (in alignment with the FDA premarketing clinical liver safety guidance).

<http://www.fda.gov/downloads/Drugs/GuidanceComplianceRegulatoryInformation/Guidances/UCM174090.pdf>.

Liver chemistry stopping criteria and required follow up assessments

Liver Chemistry Stopping Criteria – Liver Stopping Event	
ALT-absolute	ALT \geq 8xULN
ALT Increase	ALT \geq 5xULN persists for \geq 2 weeks
ALT Increase	ALT \geq 3xULN persists for \geq 4 weeks
Bilirubin^{1,2}	ALT \geq 3xULN and bilirubin \geq 2xULN (>35% direct bilirubin)
INR²	ALT \geq 3xULN and INR>1.5, if INR measured
Cannot Monitor	ALT \geq 3xULN and cannot be monitored weekly for 4 weeks
Symptomatic³	ALT \geq 3xULN associated with symptoms (new or worsening) believed to be related to liver injury or hypersensitivity

Required Actions and Follow up Assessments following ANY Liver Stopping Event

Actions	Follow Up Assessments

 • Immediately discontinue study treatment • Report the event to GSK within 24 hours • Complete the liver event CRF and complete an SAE data collection tool if the event also meets the criteria for an SAE² • Perform liver event follow up assessments • Monitor the subject until liver chemistries resolve, stabilize, or return to within baseline (see MONITORING below) • Do not restart/rechallenge subject with study treatment unless allowed per protocol and GSK Medical Governance approval is granted. • If restart/rechallenge not allowed per protocol 	
 • Viral hepatitis serology⁴ • Blood sample for pharmacokinetic (PK) analysis, obtained within 14 days after last dose⁵ • Serum creatine phosphokinase (CPK) and lactate dehydrogenase (LDH). • Fractionate bilirubin, if total bilirubin \geq 2xULN • Obtain complete blood count with differential to assess eosinophilia • Record the appearance or worsening of clinical symptoms of liver injury, or hypersensitivity, on the AE report form

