2. All events of $ALT \geq 3 \times ULN$ **and** bilirubin $\geq 2 \times ULN$ ($>35\%$ direct bilirubin) or $ALT \geq 3 \times ULN$ **and** INR >1.5 , if INR measured which may indicate severe liver injury (possible 'Hys Law'), **must be reported as an SAE (excluding studies of hepatic impairment or cirrhosis)**; INR measurement is not required and the threshold value stated will not apply to subjects receiving anticoagulants
3. New or worsening symptoms believed to be related to liver injury (such as fatigue, nausea, vomiting, right upper quadrant pain or tenderness, or jaundice) or believed to be related to hypersensitivity (such as fever, rash or eosinophilia)
4. Includes: Hepatitis A IgM antibody; Hepatitis B surface antigen and Hepatitis B Core Antibody (IgM); Hepatitis C RNA; Cytomegalovirus IgM antibody; Epstein-Barr viral capsid antigen IgM antibody (or if unavailable, obtain heterophile antibody or monospot testing); Hepatitis E IgM antibody
5. PK sample may not be required for subjects known to be receiving placebo or non-GSK comparator treatments.) Record the date/time of the PK blood sample draw and the date/time of the last dose of study treatment prior to blood sample draw on the CRF. If the date or time of the last dose is unclear, provide the subject's best approximation. If the date/time of the last dose cannot be approximated OR a PK sample cannot be collected in the time period indicated above, do not obtain a PK sample. Instructions for sample handling and shipping are in the SRM.

Liver chemistry increased monitoring criteria with continued therapy

Liver Chemistry Increased Monitoring Criteria – Liver Monitoring Event	
Criteria	Actions
ALT \geq 3xULN and <5xULN and bilirubin <2xULN, without symptoms believed to be related to liver injury or hypersensitivity, and who can be monitored weekly for 4 weeks	
 Notify the GSK medical monitor within 24 hours of learning of the abnormality to discuss subject safety. Subject can continue study treatment Subject must return weekly for repeat liver chemistries (ALT, AST, alkaline phosphatase, bilirubin) until they resolve, stabilise or return to within baseline If at any time subject meets the liver chemistry stopping criteria, proceed as described above If, after 4 weeks of monitoring, ALT <3xULN and bilirubin <2xULN, monitor subjects twice monthly until liver chemistries normalize or return to within baseline.

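### Exclusion 12 joins the ALT and bilirubin limits with *and*, so read literally a raised ALT alone does not exclude and the isolated-bilirubin exception has no function

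*Protocol*

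**What the plan says.** Section 6.2 excludes a participant who meets any one of the numbered criteria. Exclusion 12 opens: "Participants with values outside the specified ranges for the following Key Clinical Laboratory Tests must be excluded from the study". Its liver bullet reads "ALT $>2\times$ ULN and bilirubin $>1.5\times$ ULN (isolated bilirubin $>1.5\times$ ULN is acceptable if bilirubin is fractionated and direct bilirubin" is below 35%). The other bullets (GFR, HbA1c, haemoglobin, PSA) each give a limit that excludes on its own.

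Two other exclusions concern the liver, and neither gives an ALT figure. Exclusion 3 covers "Current or chronic history of liver disease, or known hepatic or biliary abnormalities", apart from Gilbert's syndrome and asymptomatic gallstones. Exclusion 13 covers hepatitis B and C.

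Section 9 states: "All screening evaluations must be completed and reviewed to confirm that potential participants meet all eligibility criteria". Section 6 rules out waivers and requires the criteria to be followed as they are stated.

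Section 3.3.1 lists as its first risk "Elevation of Alanine Aminotransferase (ALT) and other liver function tests (AST, bilirubin, total and direct"), and records that "Transient elevations in ALT without concomitant changes in bilirubin were observed in Phase 1b".

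**The concern.** With *and* between the limits, both must be exceeded before the bullet applies. A participant with ALT well above 2xULN and bilirubin at or below 1.5xULN passes it. A multicentre trial that forbids waivers depends on the literal text, so one site could apply *and* and another *or*, each believing it complies.

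At stake is the safety of a few individuals. A site following the literal wording could randomise someone whose ALT already lies in the Appendix 4 monitoring range, or even at the single-value stopping level of 8xULN. Because the on-study rules are multiples of ULN and take no account of baseline, that person could meet a stopping rule with no drug effect. Restart after liver stopping is barred (8.1.4), stopping treatment means leaving the study (8.1.3), and the only remaining scheduled visit is a safety follow-up (8.1).

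**Working it through.** No sample size, power or error-rate figure is involved, so there is no plan figure to reproduce. The check is logical, with one small count of days.

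**1. What the bullet excludes under each reading.** Let A = ALT above 2xULN, B = bilirubin above 1.5xULN, D = direct bilirubin below 35% on fractionation. The exception applies when B and D hold and A does not. In the table, 1 means yes or excluded.

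| A | B | D | *A and B* | *A and B*, with exception | *A or B* | *A or B*, with exception |
|---|---|---|---|---|---|---|
| 0 | 0 | 0 | 0 | 0 | 0 | 0 |
| 0 | 0 | 1 | 0 | 0 | 0 | 0 |
| 0 | 1 | 0 | 0 | 0 | 1 | 1 |
| 0 | 1 | 1 | 0 | 0 | 1 | 0 |
| 1 | 0 | 0 | 0 | 0 | 1 | 1 |
| 1 | 0 | 1 | 0 | 0 | 1 | 1 |
| 1 | 1 | 0 | 1 | 1 | 1 | 1 |
| 1 | 1 | 1 | 1 | 1 | 1 | 1 |

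Under *and*, only the two rows with both values raised are excluded. Isolated raised ALT (rows 5 and 6) is never excluded, and adding the exception changes 0 of 8 rows. Under *or*, isolated raised ALT is excluded and the exception changes exactly 1 of 8 rows (row 4). The bracket therefore has a function only if each limit excludes on its own.

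**2. Whether another rule fills the gap.** Exclusion 3 needs liver disease or a known abnormality and sets no number. Exclusion 13 is confined to viral hepatitis. Per-protocol criterion 09 in SAP 12.1.1 only cites exclusions 12 and 13 by number, so it inherits the ambiguity. The amendment summary records no correction.

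**3. How the gap meets the on-study rules.** The literal text admits any ALT above 2xULN with bilirubin at or below 1.5xULN. Appendix 4 starts monitoring at "ALT \geq 3xULN and <5xULN and bilirubin <2xULN", which such a participant could already satisfy at entry. Treatment stops on ALT alone at 8xULN or more, when "ALT \geq 5xULN persists for \geq 2 weeks", or when 3xULN or more lasts 4 weeks.

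SAP 12.6.1 makes the first dose Day 1. Counting time on treatment only, and assuming ALT stays at the stated level:

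- 5xULN or more: 1 + 14 = Day 15
- 3xULN or more: 1 + 28 = Day 29

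**4. Safeguards.** The Schedule of Activities has liver chemistry at screening and Day 1 (2 before dosing), then at Days 14, 28, 56, 90 and follow-up (5 after first dose). Appendix 4 adds weekly repeats from 3xULN. From 5xULN it asks for a repeat after 2–3 days and then every 2–4 days.

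**The case against.** The strongest reply is that the intended meaning is plain. The lead-in speaks of ranges for each test, and a reading that empties the line's own bracket is not the natural one. The documents use *and* loosely elsewhere: per-protocol criterion 03 in SAP 12.1.1 describes a chair-stand score below 1 and above 3, which is impossible if taken literally. An investigator seeing ALT at 8xULN on the screening report could reasonably treat it as a known hepatic abnormality under exclusion 3. There are two liver tests before or at first dose. After a liver stopping event, Appendix 4 requires liver work-up and weekly or twice-weekly monitoring until the values settle, so such a participant is not left with the follow-up visit alone. The Phase 1b elevations arose on treatment, and an entry limit could not have prevented them. The Day 15 and Day 29 figures restate the 2- and 4-week rules under an assumed constant ALT and say nothing about how often this would happen.

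Most of this stands, and it limits the harm. It does not supply the missing limit. Inferring intent is not the same as applying the stated criterion, exclusion 3 leaves the threshold to judgement, and the two pre-dose tests have no ALT-only entry limit to be compared with. Monitoring after dosing is not an entry rule. The Phase 1b observation shows only that ALT can rise without bilirubin, so bilirubin cannot be relied on to flag a raised ALT.

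**Conclusion.** The concern holds. The bullet is wrong as written: a drafting error in an operative safety eligibility rule. On the literal text an isolated ALT above 2xULN is not excluded and the bilirubin exception is empty. That conclusion rests on the wording alone and is firm.

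The consequence is plausible but bounded. It requires a site to follow the literal text and not to invoke exclusion 3. The documents give no rate of isolated ALT above 2xULN at screening, so the number affected is unknown. The Day 15 and Day 29 dates hold only if ALT stays constant on treatment. No effect on sample size, precision or the primary analysis is claimed. The change should be made because the drug's first-listed risk is ALT elevation and the correction is nearly free.

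**What to change.** Replace the bullet in exclusion 12 with two, each excluding on its own:

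- ALT above 2xULN.
- Bilirubin above 1.5xULN, except that an isolated elevation is acceptable if bilirubin is fractionated and the direct fraction is below 35%.

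Per-protocol criterion 09 in the SAP refers to the exclusion by number and needs no separate edit. The cost is one line of protocol wording and possibly a few more screen failures.
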